	
 1. Rate of adoption [proportion of PHCs that adopted TASSH at 12 months] and sustainability [maintenance of the uptake of TASSH at 24 months, one year after completion of the trial]. Adoption will be based on a composite measure of adoption ratings to assess the degree to which the three essential elements of the TASSH protocol (identification and screening of patients for HTN; proportion of patients who received lifestyle counseling by the HIV clinic nurses; and proportion of HTN patients referred for initiation of antihypertensive medication treatment). 2. The mediators of adoption and sustainability of TASSH across the primary health centers (PHCs) at 12 and 24 months.
Study Duration	24 months
Participant Duration	12 months
Population	HIV patients with uncontrolled hypertension who are 18 years and older attending one of the 30 PHCs.
Study Sites	30 Primary Healthcare Centers
Number of Participants	960 HIV+ patients with uncontrolled HTN
Description of Study Agent/ Procedure	Practice Facilitation
Reference Therapy	TASSH but no practice facilitation
Key Procedures	Ongoing external support from Practice Facilitators Intervention
Statistical Analysis	
Analysis for Aim 1: Qualitative Data Analysis for the Pre-Implementation Phase
 
Analysis for Aim 2 will consist of a repeated measures mixed-effects model for systolic BP (SBP), with fixed effects for time and intervention arm, and random effects for clinic.
 
Analysis for Aim 3: The qualitative components of sustainability at 24 months will be assessed using interviews with nurses and clinic leadership. These interviews will be recorded, transcribed and entered into NVIVO Version 11 for analysis.

Schematic of Study Design

Figure 1. Study Design

Section 1: Summary of the Study

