The study implementation phase will be conducted at 30 HIV clinics located in Lagos, Nigeria. Sites and participants for the proposed study will be recruited from the list of over 67 HIV clinics registered with the Lagos State Healthcare Board. The NIMR will recruit 960 patients from 30 HIV clinics from this list under the guidance of Lagos State AIDS Control Agency, which funds comprehensive care for its HIV patient network in Lagos State. Note that this means recruitment of about 32 participants at each of the HIV clinics. Eligibility criteria for study participants are outlined below.

Inclusion criteria

- Be an adult aged 18 years and older.
- Attends one of the 30 HIV clinics.
- Have a diagnosis of HTN with uncontrolled blood pressure, i.e. BP is 140-179/90-100 mm Hg.
- Ability to provide consent.

Exclusion criteria

- BP>180/110 mm Hg;
- history of chronic kidney disease, heart disease, diabetes
- Stroke,
- pregnancy
- Inability to provide informed consent.
- Refusal to participate in the study.

Screen Failures

Screen failures will be referred to the PHCs for further management as is done in routine practice.

Strategies for Recruitment and Retention

The research staff will conduct the screening, consent, enrollment, and all study assessments. The study will recruit 30 HIV clinics from the network of 67 HIV clinics, who are part of the 100 primary care practices managed by the Lagos State Healthcare Board (LSPHB). All 67 HIV clinics are affiliated with the Lagos State AIDS Control Agency, which utilizes LSPHB to provide comprehensive primary care services to PLWH. Eligible HIV clinics will be selected from areas geographically distinct from one another. Once a clinic agrees to participate, their director will be asked to sign an MOU and identify 2 HIV nurses to be trained. Eligible patients will be identified from the HIV clinics during routine visits. Each clinic will recruit 32 patients using these inclusion criteria: 1) patient receiving care at the clinic; 2) adults 40 years and older; 3) BP 140-179/90-100 mm Hg; and 4) can provide informed consent. Exclusion criteria: 1) BP>180/110 mm Hg; history of chronic kidney disease, heart disease, diabetes or stroke, pregnancy; 2) inability to provide consent; and 3) refusal to participate.

SECTION 4: Study Intervention

Description of Study Intervention and its Administration

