All 30 HIV clinics enrolled will begin the study as part of the pre-implementation phase for 12 months, after which they will be randomly assigned to either the PF intervention (N=15) or the self-directed condition (N=15). Once randomized, the PHCs will participate in the 12- month implementation phase (intervention period) followed by a 12-month post- implementation period to assess its sustainability.

Randomization will occur in 5 cohorts of 6 PHCs every 6 months for 30 months and will be stratified by cohort to ensure balance over time. Upon completion of recruitment for each cohort, the clinics will be randomized in a 1:1 ratio to either the PF intervention or self-directed condition (i.e. receipt of information on TASSH implementation without PF). The sequence of randomization will be generated by [name], and kept in secure electronic format inaccessible to study sites, in accordance with CONSORT guidelines. Sites will be

informed of their randomization group by telephone. Because of the nature of the intervention, it is impossible to blind the patients, lay health advisors, and the study coordinators to the group assignment. The data analysts will remain blinded to treatment assignment until the completion of the implementation phase, defined as the period from baseline to 12-month follow-up(primary endpoint). During the post-implementation phase, the practice facilitators will leave the intervention sites and will have minor direct influence on the TASSH adoption. As the intervention concludes, data analysts will be unblinded following the primary endpoint. Preliminary database containing baseline and 12-month follow-up data will be locked upon unblinding for analysis.

Study intervention compliance (Group A).

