This trial employs an effectiveness-implementation hybrid design examining the adoption of the TASSH intervention with a culturally tailored PF intervention for uptake in usual care for HIV treatment. Aim 1 will employ qualitative methods to explore inner setting variables, intervention characteristics, and implementation processes likely to influence successful uptake and sustainability of TASSH at participating PHCs. The goal of Aim 2 will be to determine the effect of the PF intervention on systolic BP reduction at 12 months (primary outcome) - the measure of clinical effectiveness of the PF intervention. It will be assessed as the mean change in systolic BP from baseline to 12 months. BP will be taken with valid automated BP device similar to our other trial.

Aim 3 will evaluate the difference between the intervention arms in adoption and sustainability of the TASSH program at 12 and 24 months. For analyses on this aim, a multilevel mixed model using an unstructured covariance matrix will be applied, with the outcomes defined as the proportion of participants within clinic who were diagnosed with HTN, received lifestyle counseling and treatment for HTN at 12 months (adoption) and the proportion of participants within clinic who have received screening, counseling and HTN treatment at 24 months (sustainability). Aim 4 will examine the mediators of adoption and sustainability of the PF intervention at 12 and 24 months.

Additional details regarding each of these analyses are discussed below.

Analysis for Aim 1: Qualitative Data Analysis for the Pre-Implementation Phase

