determined. A detailed analysis of the interviews should generate a conceptual model that elucidates barriers and facilitators of the uptake of TASSH within participating HIV clinics in Nigeria. It should also suggest modified facilitation strategies tailored to the clinics' context to overcome these challenges.

Analysis for Aim 2

Analysis for Aim 2 will consist of a repeated measures mixed-effects model for systolic BP (SBP), with fixed effects for time and intervention arm, and random effects for clinic. An interaction term be included for the intervention arm and time; this interaction, if non-zero, will indicate that the degree of change of SBP over time differs for those in the practice facilitation intervention compared to those in the self-directed condition. Also, for this aim assessments will include whether adjustment for any baseline characteristics is necessary, including such adjustments based on the change-in-estimate criteria.

Analysis for Aim 3

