For adoption, the analysis will have one within person factor – Time (baseline and 12-month coded naturally as months [0 and 12]) – and one primary between-patient factor – (Randomization Group dummy coded as 0 = Self-directed Condition and 1 = Practice Facilitation). Fixed effects will be specified for time, randomization group and their interaction effect (group by time). The outcome measure will be a composite index for adoption of TASSH (defined as patients diagnosed with HTN, received lifestyle counseling and treatment for HTN by the HIV nurses). Additionally, the nurses will be nested within clinics creating a 3-level analytic model (observations nested within nurses nested within clinics). Random effects will be specified for clinics and for nurses, adjusting for the clustering of measures within nurse and nurses within clinic. Multilevel modeling software (SAS, Version 9, PROC MIXED) will be used to compute full information maximum likelihood (FIML) estimates of the model parameters. The PROC MIXED procedure will use an error structure that allows for the possibility of group differences in (a) the error variances at 12 months; and (b) the serial correlations of the baseline with the 12-month outcomes. For sustainability, the analysis will be repeated as described above but will be evaluated at 24 months instead of 12 months. Adoption at 12 months will be assessed using questionnaires completed by nurses and sustainability at 24 months will be assessed with site interviews and site visits. Levels of adoption and sustainability will be compared between the group that randomized to the PF intervention and the group randomized to the self-directed condition. The qualitative components of sustainability at 24 months will be assessed using interviews with nurses and clinic leadership. These interviews will be recorded, transcribed and entered into NVIVO Version 11 for analysis. The analytic plan will be similar to the qualitative methods described for Aim 1.

Analysis for Aim 4

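### The Aim 2 model names only random effects for clinic; read as a clinic intercept, it leaves clinic-to-clinic variation in SBP change out of the primary test

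*Combined protocol and SAP*

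**What the plan says.** Section 6, Analysis for Aim 2, describes the primary model as a "repeated measures mixed-effects model for systolic BP (SBP), with fixed effects for time and intervention arm, and random effects for clinic". It adds an arm-by-time interaction and treats a non-zero interaction as evidence that SBP change differs between arms. The Statistical Analysis row of the Protocol Summary repeats the description ("with fixed effects for time and intervention arm, and random effects for clinic") and adds nothing to it. Neither place says whether the clinic effects are an intercept only or also vary with time. Neither names a within-patient covariance, the visits that enter, or the degrees of freedom.

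More detail is given for Aim 3. The overview in the data analysis section says "For analyses on this aim, a multilevel mixed model using an unstructured covariance matrix will be applied", where the aim meant is Aim 3. The Analysis for Aim 3 adds: "Random effects will be specified for clinics and for nurses, adjusting for the clustering of measures within nurse and nurses within clinic". Time coding and a residual structure are also set out there. None of this is carried over to Aim 2.

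Under Randomization in Section 4, clinics are the unit of randomisation, 15 per arm, in five cohorts of six, and allocation "will be stratified by cohort to ensure balance over time". On cluster size, Section 3 says: "Note that this means recruitment of about 32 participants at each of the HIV clinics". The primary outcome in Sections 3 and 6 is the change in SBP between baseline and month 12.

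**The concern.** Because clinics are randomised, the arm difference in SBP change has to be judged against how much clinics differ in SBP change. A clinic intercept takes the same value at baseline and at month 12, so it drops out of every within-patient difference and adds nothing to the variance of the interaction estimate. If it is the only clinic term, the interaction is tested against variation between patients, as though patients had been randomised.

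Some variation between clinics in change is what the trial itself expects. Hypothesis 3 and Aim 4 hold that clinic climate, leadership and culture influence adoption, and Aim 4 then relates adoption to SBP reduction.

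The effect estimate is hardly touched; the standard error and p-value are. In four data sets simulated at an ICC of change of 0.05 and a within-patient correlation of 0.5, the interaction estimate was the same under each model. Its standard error was 0.063 to 0.067 with clinic and patient intercepts, and 0.094 to 0.128 with a clinic-by-time effect added. A choice that decides significance without moving the estimate should not be open once the analysts know the arms.

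**Working it through.** **Inputs from the documents.** 30 clinics, 15 per arm; 32 patients per clinic (30 × 32 = 960, which reproduces the stated total); outcome: change between two visits, baseline and month 12.

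**Assumed, because the documents give none.** Two-sided 5% test; ICC of SBP change from 0 to 0.10; within-patient correlation r = 0.5 where it is needed; equal clinics and complete data.

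**Step 1: ordinary reading (clinic intercept, within-patient correlation modelled).** The true variance of the arm difference in mean change, divided by the variance the model reports, is

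ratio = 1 + (32 − 1) × ICC = 1 + 31 × ICC.

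The reported standard error is too small by the factor √ratio, so the actual type I error is 2Φ(−1.96/√ratio). At ICC 0.05, for example: ratio = 1 + 31 × 0.05 = 2.55; √2.55 = 1.60; 2Φ(−1.96/1.60) = 22.0%.

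**Step 2: clinic intercept only, residuals independent.** The model now takes the variance of a patient's change as 2σ² when it is 2σ²(1 − r). The ratio becomes (1 − r)(1 + 31 × ICC), that is 0.5 × (1 + 31 × ICC) at r = 0.5. It equals 1 at ICC = 1/31, about 0.03; below that the test is conservative, above it liberal.

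| ICC of change | Ratio, step 1 | True / reported SE, step 1 | Type I error, step 1 | Type I error, step 2 |
|---|---|---|---|---|
| 0 | 1.00 | 1.00 | 5.0% | 0.6% |
| 0.01 | 1.31 | 1.14 | 8.7% | 1.5% |
| 0.02 | 1.62 | 1.27 | 12.4% | 2.9% |
| 0.05 | 2.55 | 1.60 | 22.0% | 8.3% |
| 0.10 | 4.10 | 2.02 | 33.3% | 17% |

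Under step 1, coverage of the 95% interval is the complement: 95.0%, 91.3%, 87.6%, 78.0% and 66.7%. The error passes 6% at ICC 0.003 and 10% at ICC 0.014.

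**Step 3: check by simulation.** With 5,000 null trials per setting, the step 1 model gave 8.4–8.8%, 11.9–12.8%, 20.7–22.5% and 33.0–34.0% at ICC 0.01, 0.02, 0.05 and 0.10. A clinic-level test on 28 df gave 4.5–5.5% throughout. Over r from 0.3 to 0.7, the step 2 model ran from 0.0% (r = 0.7, ICC 0) to 26.1% (r = 0.3, ICC 0.10). With clinics of 16 to 48 patients and 20% of month-12 values missing at random (assumed; 1,500 trials), the ordinary reading gave 4.4%, 7.9%, 11.8%, 18.3% and 31.7% across the five ICCs, so unequal clinics and random loss do not remove the problem. Informative dropout and more than two visits were not simulated.

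**Step 4: degrees of freedom and cohorts.** Without cohorts, 30 − 2 = 28 df; with five cohorts and arm, 30 − 5 − 1 = 24 df. Using z where t on 24 df applies gives 6.2%, a minor matter by itself. Adding cohort and cohort-by-time without a clinic-by-time effect leaves the error at 5.0%, 8.8%, 12.4%, 22.1% and 34.0%.

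**The case against.** The strongest reply is that the faulty model is inferred. The plan does not say intercept in the Aim 2 text, and the plural wording can include a clinic slope. A reader might infer that the plan commits to an invalid test; the documents do not support that. The Aim 3 sentence on clustering fits an intercept but would also fit an intercept with a slope, so it does not settle the matter. This objection stands, and it limits the point to a likely error.

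Second, the direction of the error depends on reading repeated measures as supplying the within-patient correlation, although no patient-level term is named either. That is the natural reading, but on the other one the test is conservative below an ICC of about 0.03. A reader might infer certain inflation; that does not follow.

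Third, every ICC is assumed. Nothing in the documents supports 0.05 or 0.10 in particular, and at 0.003 the error is only 6.1%. The 22% and 33% figures are points in a range, not predictions.

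Fourth, the primary contrast is not missing. Sections 3 and 6 name the month-12 change, and Section 4 locks a database of baseline and month-12 data for this analysis. What stays open is mainly whether month 6 enters; with only two visits, time coding does not matter.

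Finally, cohort terms and small-sample degrees of freedom are supporting practice and not the defect. What the reply does not remove is that the ordinary reading of the stated model omits the error term that the randomisation requires.

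**Conclusion.** The point holds in conditional form and should be fixed, because the validity of the primary test depends on it. On the ordinary reading, a nominal 5% test has an actual type I error between 5.0% (ICC of change 0) and 33.3% (ICC 0.10), and is already at 8.7% at ICC 0.01. If within-patient correlation is left out as well (r = 0.5), the range is about 0.6% to 17%. Either way the nominal level is not secured by what is written. These figures rest on assumed ICCs, an assumed correlation, a two-sided 5% test, two visits and 32 patients in every clinic. They do not show that the sponsor will fit a clinic intercept alone.

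On timing, Section 4 says: "The data analysts will remain blinded to treatment assignment until the completion of the implementation phase". A reader might take this to mean that the model can still be settled blind. It is a rule and does not report the trial's current status.

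**What to change.** In the Analysis for Aim 2 and in the Protocol Summary, specify:

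- a clinic-by-time random effect in addition to the clinic intercept;
- a within-patient covariance, for example unstructured;
- the month-12 arm difference in change, already the named primary outcome, as the tested contrast;
- degrees of freedom based on clinics: 28, or 24 if the five randomisation cohorts and cohort-by-time are included (a cohort main effect alone cancels from change, as the clinic intercept does);
- what is done if the clinic-by-time variance is estimated at zero, for example keeping the clinic-based degrees of freedom;
- whether month 6 enters, with time categorical if it does.

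Make the change before the analysts are unblinded, if that has not yet happened.

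The cost is SAP wording and a few lines of code, plus some apparent power. Compared with the model without clinic-by-time, the standard error is 0%, 14%, 27%, 60% or 102% larger at ICC 0, 0.01, 0.02, 0.05 or 0.10, and 24 df widens the interval by about 5% (2.06 against 1.96). The rule for a zero variance is needed because, in simulation with 24 df, the estimate was zero in about 54%, 21%, 7% and 0.2% of trials at ICC 0, 0.01, 0.02 and 0.05. Keeping the model on 24 df in those trials is slightly conservative: type I error 3.2% at ICC 0 and 4.3% at ICC 0.01.

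### The primary Aim 2 model leaves out the cohorts within which clinics are randomized, which costs power if SBP change differs between cohorts and clinic-level change is modelled

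*Combined protocol and SAP*

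**What the plan says.** Section 4 (Randomization, Measures to minimize bias, and Blinding) randomizes the clinics in 5 cohorts of 6, one cohort every 6 months for 30 months, in a 1:1 ratio. It says that randomization "will be stratified by cohort to ensure balance over time". Each cohort therefore holds 3 clinics per arm, 15 per arm in all. On clinic size, Strategies for Recruitment and Retention says "Each clinic will recruit 32 patients using these inclusion criteria".

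Statistical Considerations, Analysis for Aim 2, specifies a "repeated measures mixed-effects model for systolic BP (SBP), with fixed effects for time and intervention arm, and random effects for clinic", adds an arm-by-time interaction and tests that interaction. The Protocol Summary gives the same model without the interaction. On covariates, the Aim 2 text will assess "whether adjustment for any baseline characteristics is necessary, including such adjustments based on the change-in-estimate criteria". Cohort is not named there, among the Aim 3 fixed effects, or under the sensitivity analyses for missing data.

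For Aim 3 the plan states a covariance structure: "a multilevel mixed model using an unstructured covariance matrix will be applied". For Aim 2 it does not say whether the clinic random effects are an intercept only or also cover clinic-level change over time. It mentions no patient-level effect.

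**The concern.** The sponsor judged calendar time worth balancing, since enrolment runs for about 30 months. With 3:3 allocation inside every cohort, any cohort-wide shift in SBP change cancels from the arm difference. A model without cohort does not know this. It counts the cohort-to-cohort variation as noise between clinics, so the standard error comes out larger than the true one. The balance bought at randomization is then not used in the primary test.

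The covariate rule is unlikely to correct this. Change-in-estimate selects variables that move the arm estimate, whereas a balanced stratification factor changes the standard error and hardly moves the estimate.

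A second uncertainty lies beneath the first. Because the clinic random effects are not defined, a reader cannot tell whether the primary test is conservative or anti-conservative.

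**Working it through.** **Inputs from the documents.** 30 clinics; 5 cohorts, each 3 v 3; 32 patients per clinic (30 × 32 = 960); outcome, SBP change from baseline to 12 months. The reviewed text has no sample-size calculation to reproduce.

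**Assumed.** Two-sided 5% test; clinic ICC of change 0.01, 0.02, 0.05, 0.10; f, the share of between-clinic variance in change that lies between cohorts, 0 to 0.5; effect set to give 80% power without cohort at f = 0. Patient-level variance of change is scaled to 1.

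**Formulas, with clinic-by-visit modelled and complete equal-sized clinics.**
- Variance of a clinic mean within cohort: Vw = (1−f)·ICC + (1−ICC)/32
- Cohort mean square: Vw + 6·f·ICC
- True variance of the arm difference: 2·Vw/15
- Variance the model expects without cohort: (2/15)·[24·Vw + 4·(Vw + 6·f·ICC)]/28
- Reference distribution: t on 28 df without cohort, on 24 df with it

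**One cell by hand (ICC 0.05, f = 0.3).** Vw = 0.7 × 0.05 + 0.95/32 = 0.0647. Cohort mean square = 0.0647 + 0.09 = 0.1547. Pooled = (24 × 0.0647 + 4 × 0.1547)/28 = 0.0775. The ratio 0.0775/0.0647 is 1.20, so the model's standard error is about 9.5% too large.

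**All cells (1,000,000 draws each; simulation error about 0.1 point).** Entries are for ICC 0.01 / 0.02 / 0.05 / 0.10.

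| f | Type I error without cohort, % | Power without cohort, % | Power with cohort, % | Gap, points |
|---|---|---|---|---|
| 0 | 5.0 throughout | 80.0 | 79.5 | −0.5 |
| 0.2 | 4.5 / 4.3 / 3.9 / 3.7 | 80.7 / 81.2 / 82.0 / 82.4 | 81.4 / 82.7 / 84.6 / 85.7 | 0.7 / 1.5 / 2.6 / 3.3 |
| 0.3 | 4.3 / 4.0 / 3.4 / 3.1 | 81.1 / 81.8 / 83.0 / 83.8 | 82.4 / 84.2 / 87.1 / 88.9 | 1.3 / 2.4 / 4.1 / 5.1 |
| 0.5 | 4.0 / 3.4 / 2.5 / 2.0 | 81.9 / 83.1 / 85.2 / 86.6 | 84.4 / 87.5 / 91.9 / 94.6 | 2.5 / 4.3 / 6.8 / 8.1 |

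With cohort-by-visit and clinic-by-visit both fitted, type I error is 5.0% throughout. With 26 patients analysed per clinic the gap is 0.6 to 7.8 points. If REML sets a negative clinic-by-visit variance to zero, the gap at ICC 0.01 becomes 0.5 to 2.0 points, at ICC 0.02 it falls by at most 0.3, and at higher ICCs it does not change.

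**The same check in mmHg.** Here cohort variance is added to a fixed within-cohort ICC. Assume SD of change 20, ICC 0.02 and a true difference of 5 mmHg. At a between-cohort SD of 3 mmHg the model's SE is 1.93 against a true 1.65, type I error is 2.5%, and power is 73% against 83% with cohort. That case corresponds to f = 9/(9 + 8) = 0.53. At a cohort SD of 1 mmHg, type I error is 4.6% and power 82.5% against about 83%.

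**If the clinic effect is an intercept only (f = 0.3).** With a patient effect, type I error is 7.5 / 10.1 / 17.4 / 27.2% without cohort-by-visit and 7.6 / 10.2 / 17.8 / 28.0% with it. With no patient effect it ranges from 0.1 to 19% for within-patient correlations of 0.3 to 0.7, so the direction is undetermined.

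**Which terms matter.** One simulated data set was fitted by REML (ICC 0.05, f = 0.5, patient intercept throughout). The arm-by-time estimate was the same in all six models. With a clinic intercept, its SE was 1.183 with no cohort term, 1.183 with a cohort main effect and 1.180 with cohort-by-visit. With clinic-by-visit added, it was 1.630, 1.630 and 1.616. A cohort main effect alone does nothing to the tested contrast.

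**Would change-in-estimate select cohort?** Share of simulated trials, f from 0.2 to 0.5, thresholds assumed:

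| Threshold | Complete, equal clinics | 20% attrition | Clinic sizes 20 to 44 plus 20% attrition |
|---|---|---|---|
| 5% | 0% | at most 2.1% | 1.6 to 18% |
| 10% | 0% | at most 0.6% | 0.3 to 4.3% |
| 20% | 0% | at most 0.3% | at most 1.0% |

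**The case against.** The strongest reply is that this is a forgone gain and not a fall in power. With total ICC held fixed, stratification lowers the true variance as f rises, so power without cohort stays at or above 80% in every cell. That is right, and it is why the table prints both absolute powers. The gap is still power that the design has earned and the stated analysis does not collect.

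Second, the harm needs two conditions that the documents do not establish: cohorts must differ in SBP change, and clinic-level change must be modelled. This also stands, and the conclusion is worded conditionally. On the intercept-only reading, the missing clinic-by-visit term is a separate and larger defect. Cohort moves type I error by at most 0.8 point there, and the intercept-only figures should not be counted as harm from omitting cohort.

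Third, validity is not threatened by the omission itself. The arm estimate stays unbiased, and under the stated conditions type I error is at or below 5%. At low ICC and small f the gap is only 0.7 to 2.4 points.

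Fourth, the calculation covers baseline and 12 months, while Section 5 schedules five visits and the Aim 2 text does not say which enter the model. The cost of the extra terms with more visits and 30 clinics was not checked.

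Finally, the covariate sentence introduces change-in-estimate with the word including, so other criteria are possible. With a 5% threshold and very uneven clinics, cohort could be selected in up to 18% of trials. None of this commits the plan to including cohort.

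**Conclusion.** The concern holds. The primary model does not use the strata by which clinics are randomized, and nothing else in the plan supplies them. If clinic-level change is modelled and cohorts differ, the test is conservative (type I error 4.5 to 2.0%) and power is 0.7 to 8.1 points below that of the cohort-adjusted model, for f of 0.2 to 0.5 and ICC of 0.01 to 0.10. These inputs are all assumed. If cohorts differ little the loss is small, and the treatment estimate is not biased. This is a change the sponsor should make to an otherwise usable analysis, held with medium confidence because the size rests on unstated variances.

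A secondary point: choosing covariates by their effect on the arm estimate leaves type I error unprotected if the choice is made selectively. Section 4 says "Preliminary database containing baseline and 12-month follow-up data will be locked upon unblinding for analysis", which suggests the choice could be made with allocation known. That is an inference, because the Aim 2 text does not date the step.

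**What to change.** In Analysis for Aim 2 and in the Protocol Summary:

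- Prespecify cohort and cohort-by-visit as fixed effects.
- State that the random effects include clinic-by-visit, and test arm-by-time on between-clinic degrees of freedom.
- State which visits enter the model and how time is coded.
- List any further baseline covariates before unblinding, and move change-in-estimate to a sensitivity analysis.

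The cohort terms and the clinic-by-visit term are both needed. A cohort main effect alone leaves arm-by-time unchanged in complete data, and cohort-by-visit without clinic-by-visit does not restore type I error.

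The cost is wording only. For the baseline to 12-month comparison, cohort uses 4 of the 28 between-clinic degrees of freedom, about 0.5 point of power (80.0% to 79.5%) if cohorts turn out not to differ. If more visits are modelled, that cost should be rechecked.
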